We plan to randomize up to 110 patients with type 1 diabetes into two different treatment sequences:

Group A following the sequence $SAP \rightarrow USS+SAP(d) \rightarrow USS+CLC(d) \rightarrow USS+SAP(d)$, and **Group B** following the sequence $USS+SAP(d) \rightarrow USS+CLC(d) \rightarrow USS+SAP(d) \rightarrow SAP$.

These treatment modality sequences are presented in the figure below, and are color coded to match the color-coding of active control modules relevant to each treatment modality presented in Figure 1:

Figure 1: Design of One 11-month Study Session

Each treatment modality will continue for 8 weeks – sufficient time to address the following specific aims:

SA1: Dinner/Night CLC achieved by USS+SAP(d) will be superior to SAP alone in terms of: (1) Improved HbA1c without increasing the risk for hypoglycemia; (2) Reduced incidence and risk for hypoglycemia overnight, and (3) Reduced fear of hypoglycemia and improved diabetes quality of life scores.

SA2: CLC during the day achieved by USS+CLC(d) will preserve the benefits of USS+SAP(d) and will be superior to USS+SAP(d) in terms of: (1) Increased time within target range of 70-180mg/dl during the day; (2) Reduced risk for hypoglycemia, particularly during and after exercise, and (3) Reduced postprandial glucose variability.

SA3: CLC system acceptance evaluated by individual structured interviews and technology acceptance scores will be: (1) Superior, for USS+SAP(d) compared to SAP alone, i.e. adding USS in the evening and overnight will increase patients' acceptance of CLC, and (2) Marginally inferior, for USS+CLC(d) compared to USS+SAP(d); i.e. some patients would prefer SAP alone during the day due to perceived increased system complexity.

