1.4 Closed-Loop Control System

A general description of the Artificial Pancreas Platform devices identified below will be used in the Closed-Loop Control System. New generations of CGMs and insulin pumps with embedded inControl-AP could become available for inclusion in this trial and could be used providing these new developments do not change the core functionality of the system.

For the inControl Platform, (see Figure 4-Panel A):

- inControl Diabetes Management Platform a smart-phone Artificial Pancreas medical platform;
- CGM study CGM connected to the AP using low power Bluetooth communication protocols;
- Insulin Pump insulin pump connected to AP system via wireless Bluetooth.
- Remote Monitoring Server connected to inControl Cloud via 3G or local Wi-Fi network, and
- Modular Closed-Loop Control Algorithm Running on the AP system, which is of Controlto-Range (CTR) class

We have successfully completed a pilot study of the Tandem t:slim X2 with Control-IQ Technology. This pilot study included 5 adults (mean HbA1c 6.5%) using the system between 36-48 hours, and was successfully completed with 86% mean time in target range of 70-180 mg/dL and 2.8% median time below 70 mg/dL. The system maintained connectivity 98% of the intended

time in closed-loop. Given the positive results from this pilot study, we now plan to incorporate t:slim X2 with Control-IQ Technology in this protocol as well.

For the Tandem-G6 configuration, (see Figure 4-Panel B):

The Closed-Loop Control System contained in t-slim X2 with Control-IQ Technology is described in Master File MAF-2032/A003 and has been approved in G170255 and G170267. Control-IQ Technology is derived from inControl previously described in IDE# G160097, G160181, G150240 and G140169/S010. The CLC is an "artificial pancreas" (AP) application that uses advanced closed loop control algorithms to automatically manage blood glucose levels for people with Type 1 Diabetes. The system modulates insulin to keep blood glucose in a targeted range. The system components include the t:slim X2 with Control-IQ Technology and the Dexcom CGM G6 (Fig. 4-B).

Figure 4. AP System Components: Panel A – G4+Roche pump configuration; Panel B – G6+Tandem Control IQ

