6.1 Analysis Plan

Statistical Analysis: The overall analysis will follow Intention-to-treat approach and will use Generalized Linear Mixed Models (e.g. those available in IBM SPSS) including fixed factors following the factorial designs presented in study figure for the specific aims listed below, and random effects reflecting patients' attrition rate.

Metrics:

- (i) Five HbA1c determinations approximately 10 weeks apart;
- (ii) Eight-week sequences of CGM data accompanied by BG self-monitoring readings and recording of the timing of events such as meals and exercise through the GUI
- (iii) Psychometric questionnaires administered concurrently with HbA1c, and
- (iv) Individual structured interview and qualitative/quantitative technology acceptance assessments. CGM data will be used to compute established metrics of risk for hypoglycemia, e.g. the Low BG Index (LBGI), glucose variability, and BG dynamics, as presented in our review of statistical tools for CGM data analysis.

Primary Hypothesis by Specific Aims of the Study

Specific Aim 1: Overnight CLC achieved by USS+SAP(d) will be superior to SAP alone in terms of: (1) Improved HbA1c without increasing the risk for hypoglycemia; (2) Reduced incidence and risk for hypoglycemia overnight, and (3) Reduced fear of hypoglycemia and improved diabetes quality of life scores.

Specific Aim 2: CLC during the day achieved by USS+CLC(d) will preserve the benefits of USS+SAP(d) and will be superior to USS+SAP(d) in terms of: (1) Increased time within target range of 70-180mg/dl during the day; (2) Reduced risk for hypoglycemia during and after exercise, and (3) Reduced postprandial glucose variability.

Specific Aim 3: CLC system acceptance evaluated by an individual structured and technology acceptance scores will be: (1) Superior, for USS+SAP(d) compared to SAP alone, i.e. adding USS overnight will increase patients' acceptance of CLC, and (2) Marginally inferior, for USS+CLC(d) compared to USS+SAP(d); i.e. some patients would prefer SAP alone during the day due to perceived increased system complexity.

Primary Outcomes

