Specific Aim 1: The **primary outcome** is improvement in diabetes control on USS+SAP(d) vs. SAP alone as defined by reduced risk for hypoglycemia (Time <70 mg/dL by CGM) without increase in HbA1c. Repeated Measures ANOVA with covariate will assess this effect. Inversely, comparing HbA1c with covariate overnight Time <70 mg/dL by CGM will address SA1-2, while comparing the psychometric questionnaire scores pre-post treatment will address SA1-3.

Specific Aim 2: The **primary outcome** is improved time within the target range of 70-180mg/dl during the day on USS+ CLC(d) vs. USS+SAP(d). Repeated Measures ANOVA following the study design outlined will assess this effect. SA2-2 will be addressed

comparing frequency of hypoglycemia within the post-exercise periods recorded by the system; SA2-3 will be addressed using Variability-Grid Analysis, and SA-4 will be addressed by a sub-analysis limited to those who did not achieve HBA1c≤7.5% during the first 3 months of the study.

Specific Aim 3: will be addressed by comparing structured interviews and technology acceptance scores along the two sequences of treatment modalities specified in the study design: treatment escalation for Group A and de-escalation for Group B. Analyzing the random effect of patient attrition will shed additional light on system acceptance.

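### SA2 hypothesizes that USS+CLC(d) preserves the benefits of USS+SAP(d), but section 6.1 assigns no Time <70 mg/dL or HbA1c comparison to USS+CLC(d), so that clause cannot be answered

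*Combined protocol and SAP*

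**What the plan says.** Section 6.1 states SA2 as a hypothesis with two parts: "CLC during the day achieved by USS+CLC(d) will preserve the benefits of USS+SAP(d) and will be superior to USS+SAP(d) in terms of" daytime time in range, hypoglycemia around exercise, and postprandial variability. Section 1.1 has the same two-part form.

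The benefit to be preserved is set out under SA1 in the same section. The SA1 primary outcome is lower Time <70 mg/dL by CGM on USS+SAP(d) than on SAP, on condition that HbA1c does not increase.

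The SA2 analyses in section 6.1 are:

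- Primary: "improved time within the target range of 70-180mg/dl during the day on USS+ CLC(d) vs. USS+SAP(d". The method is given as "Repeated Measures ANOVA following the study design outlined will assess this effect".
- SA2-2: "comparing frequency of hypoglycemia within the post-exercise periods recorded by the system".
- SA2-3: Variability-Grid Analysis.
- An item labelled SA-4, a sub-analysis of participants whose HbA1c stayed above 7.5% in the first three months. HbA1c selects the subgroup here; it is not compared between modalities.

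The hypoglycemia part of SA2 is worded in three ways. Section 1.1 has "Reduced risk for hypoglycemia, particularly during and after exercise". The hypothesis in section 6.1 has "Reduced risk for hypoglycemia during and after exercise". The analysis in section 6.1 covers post-exercise periods only.

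**The concern.** The first half of the SA2 hypothesis has no analysis. SA1 pairs its primary outcome with a second condition, so that a gain on one measure cannot hide a loss on the other. SA2 has no such pairing, and the measure that defines the SA1 benefit is not carried over to USS+CLC(d).

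At stake is what may be concluded about the step from evening-and-overnight to 24-hour control. A favorable daytime time-in-range result would naturally be read together with the rest of the SA2 sentence, as if the SA1 benefit had been shown to persist. Nothing in section 6.1 would have tested that. A contrast chosen after the data are seen would be weak support for a hypothesis that the protocol states in advance.

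**Working it through.** **1. Which comparison is assigned to which aim (section 6.1)**

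| Measure | USS+SAP(d) vs SAP | USS+CLC(d) vs USS+SAP(d) | USS+CLC(d) vs SAP |
|---|---|---|---|
| Time <70 mg/dL | SA1 primary; overnight as covariate in SA1-2 | none | none |
| HbA1c | SA1 condition; SA1-2 | none | none |
| Daytime time in 70-180 | none | SA2 primary | none |
| Post-exercise hypoglycemia | none | SA2-2 | none |
| Variability grid | none | SA2-3 | none |

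The two rows that define the SA1 benefit are empty in both USS+CLC(d) columns. Section 6.1 also lists the Low BG Index among the CGM metrics to be computed, but ties it to no SA2 contrast.

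**2. Why time in range cannot stand in**

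Over any period, time below 70, time in 70-180 and time above 180 add to 100%. Hence

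change in time in range = −(change in Time <70) − (change in time >180).

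Time in range improves whenever time above 180 falls by more than Time <70 rises. As a hypothetical case, if Time <70 went from 2% to 3%, any fall of more than 1 percentage point above 180 would still give an improvement. The SA2 primary is also limited to daytime, so a change in overnight Time <70 does not enter it. SA2-2 sees only the periods after recorded exercise.

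**3. The plan's own sample size, as the basis for precision**

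Inputs from section 6.2: f = 0.2 (SA1) and 0.3 (SA2), α = 0.01, power 90%, correlation ρ = 0.4, attrition 31%, 110 randomized, 76 completing. For a within-subject repeated-measures F test with m levels, λ = f²·n·m/(1−ρ), with df m−1 and (n−1)(m−1).

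- SA1, m = 4 periods: n = 75 gives λ = 0.04 × 75 × 4 / 0.6 = 20.0 and power 0.90; n = 76 gives power 0.91. This reproduces the stated 76 to within one subject.
- Attrition: 76 / (1 − 0.31) = 110.1, against the stated 110.
- SA2 time in range as a two-condition contrast, n = 76: λ = 0.09 × 76 × 2 / 0.6 = 22.8, power 0.98. Nothing in this calculation involves Time <70.

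**4. How precisely the missing contrast could be estimated**

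The documents give no SD for Time <70 or HbA1c, so results are in units of the between-subject SD. They assume that ρ = 0.4 applies to these measures too, that the SD is equal across periods, and that differences are approximately normal.

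- USS+CLC(d) minus one USS+SAP(d) period: SD of the difference = √(2(1−0.4)) = 1.095. With n = 76, SE = 1.095/√76 = 0.126 and the 95% half-width is 1.992 × 0.126 = 0.25 SD.
- USS+CLC(d) minus the mean of the two USS+SAP(d) periods: variance = 1 + (1+0.4)/2 − 2(0.4) = 0.9, SD 0.949. With n = 76, SE = 0.109 and the half-width is 0.22 SD.
- Section 2.1 gives 64 completers where sections 1.5.1 and 6.2 give 76. With 64, the half-widths are 0.27 and 0.24 SD.

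If the sponsor wanted a formal non-inferiority test (true difference 0, one-sided 0.025, single-period contrast), 76 completers give 90% power only for a margin of about 0.41 SD. A margin of 0.3 SD would need 143 completers and one of 0.2 SD would need 318.

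**The case against.** A single time-in-range primary is a legitimate choice, and readings below 70 count against it. Hypoglycemia metrics will be computed from every eight-week CGM sequence, so a rise would be measurable. Severe hypoglycemia prompts DSMB review under section 5.10.2. By design (section 3.10), participants are in closed loop overnight in both modalities, which makes preservation of the overnight benefit plausible. All of this stands, but none of it names an analysis for the preservation clause. Time in range counts lows only as part of a net total, the Low BG Index serves no SA2 comparison, and the DSMB trigger concerns severe events rather than CGM time below 70.

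Some stronger readings are tempting and are not supported:

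- *SA2 would be declared met while hypoglycemia rises.* The documents contain no aim-level success rule. They name a primary outcome and separate sub-aim analyses.
- *More daytime closed loop is likely to raise Time <70.* A model that lowers mean glucose at a fixed coefficient of variation produces such a rise by construction. For the mean glucose values in the adult overnight pilot in section 1.2 (170.3 and 139.0 mg/dL), a lognormal model at 36% predicts a rise from 0.9% to 3.7%. The pilot itself saw a fall from 1.56% to 0.55% (p = 0.06).
- *The Control-IQ pilot is a warning sign.* Section 1.4 reports "86% mean time in target range of 70-180 mg/dL and 2.8% median time below 70 mg/dL", but in 5 adults over 36-48 hours with no comparator. It cannot be set against the overnight crossover pilot, which differs in system, time of day, duration and summary statistic.
- *SA2 should require USS+CLC(d) to beat SAP on Time <70.* That would not test preservation. With hypothetical values of 4% on SAP, 2% on USS+SAP(d) and 3% on USS+CLC(d), half the benefit is lost and the condition could still be met.

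**Conclusion.** The point holds as a gap between hypothesis and analysis. SA2 states that the USS+SAP(d) benefits are preserved, SA1 defines the main one through Time <70 and HbA1c, and section 6.1 compares neither on USS+CLC(d). The plan as written therefore cannot support the preservation clause, whatever the time-in-range result. This rests on the text and on the identity in step 2, not on any assumed effect.

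The documents provide no basis for sizing a rise in hypoglycemia or for saying that one is expected. What can be sized is the precision available for the missing contrast: a 95% half-width of about 0.25 SD with 76 completers, or 0.22 to 0.27 SD across the cases shown, given the assumptions in step 4. That is enough for an informative interval but not for a tight non-inferiority margin. The change should be made; it does not call the SA2 primary outcome itself into question.

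**What to change.** In section 6.1, under SA2:

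1. Prespecify the USS+CLC(d) minus USS+SAP(d) difference in Time <70 mg/dL over 24 hours, with overnight and daytime shown separately, and the same difference in HbA1c. Estimate each with a confidence interval from the mixed model named at the start of section 6.1. Say whether one or both USS+SAP(d) periods are used.
2. Give the same measures for USS+CLC(d) vs SAP as supporting contrasts.
3. State that any conclusion on preserved benefits rests on these intervals and not on the time-in-range result. A formal non-inferiority margin is optional and would be for the sponsor to justify.
4. Reconcile SA2-2 across section 1.1, the hypothesis in section 6.1 and its analysis, so that all three cover the same periods.

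The cost is wording and a few extra contrasts from CGM and HbA1c data already collected in every phase. The drawback is that the preservation statement may turn out less favorable, or inconclusive.

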6.2 Sample Size

Sample Size Determination is based on our pilot studies of overnight CLC. We conservatively estimate that the effect size of USS+SAP(d) vs. SAP will be $f \ge 0.2$. Power calculations (G*Power 3) assuming $\alpha = 0.01$, 90% power, correlation of 0.4 between the repeated measures, and attrition of up to 31% yield a sample size of **N=110** subjects to be randomized at baseline, with N=76 subjects completing the study. For SA2 using USS+CLC(d), our pilot data with this same system during the day indicate a larger effect size f=0.3. For SA-3, the expected effect size is f=0.35-0.4 based on our previous interviews. Thus, a sample size that is adequate for SA-1 will have adequate power to address SA-2 and SA-3 as well.

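### SA1 and SA2 are two-modality claims, but 6.1 names no contrast; if the overall repeated-measures F is used, SA2 can reach significance because SAP differs

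*Combined protocol and SAP*

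**What the plan says.** Section 6.1 (Primary Outcomes) defines each primary outcome as a comparison of two modalities: for SA1, USS+SAP(d) against SAP on CGM time below 70 mg/dL, provided HbA1c does not rise; for SA2, USS+CLC(d) against USS+SAP(d) on daytime time in 70-180 mg/dL.

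The SA1 test is a repeated measures ANOVA with a covariate. For SA2, "Repeated Measures ANOVA following the study design outlined will assess this effect". The opening of 6.1 plans mixed models "including fixed factors following the factorial designs presented in study figure for the specific aims listed below". The design (sections 1.1 and 3.7) has two sequences of four 8-week phases:

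- Group A: SAP, USS+SAP(d), USS+CLC(d), USS+SAP(d)
- Group B: USS+SAP(d), USS+CLC(d), USS+SAP(d), SAP

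No section names a pairwise contrast, says how the two USS+SAP(d) phases are combined, says which F-test decides, or gives a direction.

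Section 6.2 states the SA1 effect for the pair of modalities ("We conservatively estimate that the effect size of USS+SAP(d) vs. SAP will be" at least f=0.2). It then uses alpha 0.01 and "90% power, correlation of 0.4 between the repeated measures" to reach 110 randomized, "with N=76 subjects completing the study". For SA2, "our pilot data with this same system during the day indicate a larger effect size f=0.3".

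**The concern.** An overall F from the four-phase design has the null hypothesis that all phase means (or all modality means, or all group-by-phase terms) are equal. That is not the null of either aim. SAP sits in phase 1 for Group A and phase 4 for Group B, so a SAP difference feeds into both the phase effect and the group-by-phase effect. If such an F were taken as the SA2 test, it could reject because SAP is worse, with daytime closed loop adding nothing. SA2 exists to answer whether daytime closed loop adds anything.

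The plan also leaves several F-tests and contrasts open to choice once the data are in hand, and the power in 6.2 may not belong to the comparison that each aim makes.

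**Working it through.** **1. Which test gives 76 completers?** Inputs from 6.2: f=0.2, alpha=0.01, power 90%, correlation rho=0.4; two groups from 1.1. For a repeated-measures F with m measurements under sphericity, lambda = N·m·f²/(1−rho), with df m−1 and (N−2)(m−1).

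| m | N for 90% | power at N=76 |
|---|---|---|
| 2 | 115 | 0.704 |
| 3 | 90 | 0.829 |
| 4 | 75 (76 in equal groups) | 0.909 |
| 5 | 64 | 0.954 |

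At m=4 and N=76, lambda = 76×4×0.04/0.6 = 20.27. The within-between interaction gives the same N. Attrition: 110×0.69 = 75.9. The stated figures therefore reproduce with four measurements and not with two.

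**2. How a SAP difference enters the overall F.** Let the SA2 null hold and let SAP be lower by d SD.

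- Phase means over both groups are −d/2, 0, 0, −d/2. Squared deviations from their mean sum to d²/4, so lambda = 76·(d²/4)/0.6.
- Half the Group A minus Group B differences are −d/2, 0, 0, +d/2. Their squares sum to d²/2, so lambda = 76·(d²/2)/0.6.

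Both tests have 3 and 222 df. At d=0.4, lambda is 5.07 and 10.13. At d=0.2, it is 1.27 and 2.53.

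**3. Rejection with the SA2 null true.** Assumption: d = 0.2 to 0.4 SD in daytime time in range. The upper value is the two-mean equivalent of f=0.2 (d=2f), which 6.2 states for SA1 and not for this endpoint. The first two columns follow from step 2. The three-modality F (the two USS+SAP(d) phases averaged) and the directional rates are simulated with 38 per group, rho=0.4 and alpha=0.01, to within about one percentage point.

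| SAP deficit | phase F | group-by-phase F | three-modality F | SA2 contrast |
|---|---|---|---|---|
| 0 | 1% | 1% | 1% | 1% |
| 0.2 SD | 4% | 9% | 20-21% | 1% |
| 0.4 SD | 22% | 53-54% | 84-85% | 1% |
| 0.2 SD, USS+CLC(d) ahead | 3% | 3% | 12% | |
| 0.4 SD, USS+CLC(d) ahead | 15% | 22% | 44% | |

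**4. Power of the named contrasts at 76 completers, alpha 0.01 two-sided.** Here lambda = 76·d²/v with 1 and 74 df, where v is the within-subject variance of the contrast in SD² units. With one USS+SAP(d) phase, v = 2×0.6 = 1.2. With the plain mean of both, v = 1.5×0.6 = 0.9.

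| Aim | v=1.2 | v=0.9 |
|---|---|---|
| SA1, d=0.4 (f=0.2) | lambda 10.13, power 0.704 | lambda 13.51, power 0.845 |
| SA2, d=0.6 (f=0.3) | lambda 22.8, power 0.982 | lambda 30.4, power 0.998 |

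For 90% power, SA1 needs 115 completers (116 in equal groups, about 169 randomized) or 88 (about 128 randomized).

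**5. Effect of phase terms.** Write D1 to D4 for Group A minus Group B at each phase. Phase effects cancel in these differences, and the SA1 estimate becomes (D4−D1)/2, that is, half of (A4−A1)−(B4−B1). Its variance is (1/4)·2·[2(1−rho)/38] = 2(1−rho)/76 = 1.2/76. SA2 likewise becomes (D3−D2)/2 with the same variance. So once phase is fitted, the second USS+SAP(d) phase brings no gain, and the v=1.2 column applies: SA1 about 70%, SA2 about 98%.

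**The case against.** The strongest reply is that 6.1 says the ANOVA assesses this effect, and the effect just named is the pairwise one. A modality contrast inside the ANOVA or mixed model fits that text. This stands. A reader might infer that the plan makes an overall F the decision rule, but no section says so. The defect is that nothing is specified.

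The wording about following the study design is attached to SA2 only. For SA1 the four-phase reading comes from 6.2 alone, and a power shortcut is not an analysis rule. Section 2.1 also mentions 64 completers and an increase for new devices. In step 1, 64 is the m=5 result, which would match the five HbA1c determinations in 6.1. So 76 may be an enlarged target and not the output of an m=4 calculation. Either way, the arithmetic points to more than two levels.

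A reader might also infer that SA2 is likely to be a false positive. The documents do not support that. By day, SAP and USS+SAP(d) are both open loop (1.5.2), so the daytime difference may be small. Section 1.2 expects better days after well-controlled nights but gives no figure for this comparison. The highest rates belong to a three-modality F that the plan does not name, and all rates are lower when USS+CLC(d) must be ahead.

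Lack of direction is not a separate fault: a two-sided contrast is adequate if success also requires the estimate to favour the claimed modality.

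**Conclusion.** The concern holds as a gap in the primary analysis with measurable consequences. Each aim needs a pairwise contrast and none is named, while the completer number in 6.2 fits a four-measurement F and not a two-modality test.

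If an overall F were used, the SA2 error rate would exceed 1% by an amount that depends on the unknown daytime SAP difference. Over 0.2 to 0.4 SD it runs from about 4% to about 85% across the three candidate F-tests, or from about 3% to 44% when USS+CLC(d) must be ahead. With no SAP difference it stays at 1%. The SA2 contrast stays at 1% throughout. These figures assume 76 completers, rho=0.4 and sphericity.

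Separately from which test was intended, SA1's own comparison has about 70% to 85% power at 76 completers under the plan's inputs, not 90%. SA2 keeps at least 98%.

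**What to change.** In 6.1, name one single-degree-of-freedom within-subject contrast per aim: USS+SAP(d) minus SAP for SA1, and USS+CLC(d) minus USS+SAP(d) for SA2. Estimate both from the mixed model with modality, phase, sequence and subject terms, with the two USS+SAP(d) phases combined as one modality level. Test each at two-sided alpha 0.01 with its confidence interval, and require the estimate to favour the claimed modality. Keep SA1's covariate and its condition that HbA1c does not increase. State that the overall F-tests decide neither aim.

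In 6.2, restate the power at 76 completers for these contrasts. For SA1 it is about 85% if both USS+SAP(d) phases are averaged without phase adjustment, and about 70% if one phase is used or phase terms are fitted. For SA2 it is at least 98% either way. Say which model the figure belongs to.

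The cost is a change of wording with the same data and model family. The downside is a less favourable SA1 power figure, which the sponsor must either accept and state or address through the sample size.

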The subject must be able to complete system-related tasks independently to be eligible to continue in the study.

3.6 Visit 5 - AP System Run-In phase: Home Use in Pump Only (Open Loop) Configuration

Eligible subjects who have not had recent use of the system (more than ~2 weeks of use in the past 6 months or more than ~2 months of use in the past year) will complete up to 2-week home use period with the full system in pump only (open loop) configuration where no closed loop algorithms are activated. Subject will be instructed not to start closed loop during this run-in phase. Subjects who have had prior experience with the AP system as defined above will not be required to do Visit 5. Subjects who are demonstrating proficiency, as determined by the study physician, may have a shorter open loop run-in phase with a minimum of 5 days duration Criteria for proficiency is listed in section 3.11.

For the inControl system, remote monitoring will be available during this period for the purposes of data collection and ad hoc assessment of system performance by study team. The study team will be available for the subject to contact during this phase. Study staff will contact the subject and review data on the Remote Monitoring once daily. The subject may contact the study staff at any time.

For the Tandem-G6 system, remote monitoring will not be available. Study staff will contact the subject daily to assess difficulties with the use of the system. The subject may contact the study staff at any time. If the study team requires additional information, the subject may be asked to upload the pump at home so that the study can review data on the t:connect website.

3.7 Visit 6 + Visit 7 + Visit 8 Washout Following Completion of the Each Study Phase

At the completion of the each phase of the study, subjects will have up to a two week washout prior to proceeding to the next phase.

First Phase: Group A 8 weeks of SAP; Group B 8 weeks of USS +SAP(d) Second Phase: Group A 8 weeks of USS +SAP(d); Group B 8 weeks of USS + CLC(d) Third Phase: Group A 8 weeks of USS + CLC(d); Group B 8 weeks of USS +SAP (d) Fourth Phase: Group A 8 weeks of USS + SAP(d); Group B 8 weeks of SAP

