Visit 6 may occur concurrently with Visits 3, 4 and 5. During this time, subjects may continue on the study pump if Visit 4 has been completed or switch to their own personal pump. Subjects will either come to the study site or complete the following locally: HgbA1c, and psychometric questionnaires (Appendix A-11)

Individual Structured Interviews [Optional]: Subjects will be asked to participate in an individual structured interview after using the AP system (Group A= after visit 7, 8, 9; Group B=after visit 6, 7, 8).

These structured interviews will be audiotaped to assist staff in recording subjects' responses. These interviews may be conducted in person or over the phone. The audio recordings will be labeled with the study subject ID number and will be stored with other study documentation.

Data will be downloaded from study devices, glucometer and personal pump (during SAP) by one of several methods: locally by the subject and sent to study staff, by study staff at time of a visit or devices not in use being mailed to the study staff for downloading.

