3.8 Visit 9 - End of Study Visit

At the completion of the final phase of the study, subjects will complete their final visit. Subjects will resume their personal pump. Subjects will either come to the study site or complete the following locally: HgbA1c, questionnaires, and may participate in an individual structured interview.

Data will be downloaded from study equipment, glucometer and personal pump (during SAP) by one of several methods: locally by the subject and sent to study staff, by study staff at time of a visit or equipment mailed to the study staff for downloading.

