5.10 Study Stopping Criteria

5.10.1 Criteria for Individual Subjects

Rules for stopping the study for an individual subject are as follows:

- 1. System or controller malfunctions that impose on the safety of the subject, unless the problem can be clearly identified and the system definitively repaired
- 2. Two distinct episodes of severe hypoglycemia or hyperglycemia/DKA (not associated with infusion set failure) as defined in section 5.1 related to automated insulin delivery during closed loop use
- 3. The subject requests the study be stopped
- 4. Subject pregnancy
- 5. Use of oral or injectable glucocorticoids during closed-loop system operation (subject may resume study procedures once effects of glucocorticoids are no longer present)
- 6. Study staff are persistently unable to contact the subject in a timely manner during the course of the study
- 7. Persistent subject non-adherence to safety-related procedures such as frequency of fingersticks or hypoglycemia, hyperglycemia and ketone treatment instructions
- Ketones ≥ 3 mmol/L or with symptoms requiring action regardless of blood sugar or ketones (i.e. abdominal pain, vomiting illness, unable to eat or drink, fever ≥ 101.5, clinical need for Tylenol/acetaminophen, significant illness, use of epinephrine). Subject may resume study procedures once conditions or symptoms are no longer present.

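### SA3 schedules no acceptance score for subjects who leave mid-phase, and reads attrition, undivided by reason, as information on acceptance

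*Combined protocol and SAP*

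**What the plan says.** Section 6.1 compares structured interviews and technology acceptance scores along the two treatment sequences, then adds: "Analyzing the random effect of patient attrition will shed additional light on system acceptance". The general model is stated in the same section: "The overall analysis will follow Intention-to-treat approach and will use Generalized Linear Mixed Models", with random effects meant to reflect the attrition rate. No missing-data assumption is given, and attrition is not split by reason or phase.

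On timing, section 6.1 lists "Psychometric questionnaires administered concurrently with HbA1c". Section 3.7 places Visits 6 to 8 between phases: "At the completion of the each phase of the study, subjects will have up to a two week washout". At those visits, "Subjects will either come to the study site or complete the following locally: HgbA1c, and psychometric questionnaires". Section 3.8 says: "At the completion of the final phase of the study, subjects will complete their final visit". Interviews are optional and follow phases that used the system: "Subjects will be asked to participate in an individual structured interview after using the AP system" (section 3.7). Section 3.1 says of the acceptance questionnaire only that it is given at later time points once the system has been started. No exit assessment is described.

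Section 1.5.1 allows for up to 31% attrition and gives study duration as the cause. Section 5.10.1 lists eight individual stopping rules, one of which is "The subject requests the study be stopped". Under section 5.6, early withdrawals are reviewed and reasons for dropout go to the IRB each year; the SA3 analysis does not use them.

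**The concern.** SA3(2) predicts that 24-hour control is slightly less acceptable than evening and overnight control, because some subjects will find it too complex. A subject who gives up during USS+CLC(d) for that reason is the clearest instance of the prediction, yet on the schedule as written would contribute no score and no interview for that modality.

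Attrition could help fill the gap, but only if the exits that say something about the system can be told apart from those that do not. Section 6.1 does not separate them. A pregnancy, a device malfunction and a withdrawal from fatigue with a study of nearly a year would count the same as a withdrawal because the system was too burdensome. At stake is what SA3 can conclude, both from the scores and from the attrition analysis.

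**Working it through.** **The plan's own figure.** Section 6.2 has 110 randomized, 76 completing and 31% attrition. 110 × 0.69 = 75.9, and (110 − 76)/110 = 34/110 = 30.9%. The figures agree. (Section 2.1 gives about 76% completing with N=64, which does not match; 31% is used below.)

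**Power is not the issue.** For f = 0.35 to 0.4 (section 6.2), α = 0.01, correlation 0.4 and N = 76, a within-subject repeated-measures F test has power above 0.99 with 2, 3 or 4 measurements.

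**Who is missing from the SA3(2) contrast.** Group A runs SAP, USS+SAP(d), USS+CLC(d), USS+SAP(d). Group B runs USS+SAP(d), USS+CLC(d), USS+SAP(d), SAP. In both, USS+SAP(d) comes immediately before USS+CLC(d).
- Leaving before the first USS+SAP(d) assessment: neither modality is scored.
- Leaving during USS+CLC(d), or in the washout just before it: USS+SAP(d) is scored, USS+CLC(d) is not.
- Leaving later: both are scored.

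One-sided loss for this contrast therefore falls on USS+CLC(d).

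**How many.** Assume 31% loss spread evenly over four phases. Loss per phase is 1 − 0.69^(1/4) = 8.9%. Completion of phases 1 to 4 is then 91.1%, 83.1%, 75.7% and 69.0%. With 55 per group (assumed), exits during USS+CLC(d) are 55 × (0.831 − 0.757) ≈ 4.1 in Group A and 55 × (0.911 − 0.831) ≈ 4.4 in Group B, or 8 to 9 subjects.

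**If leavers are less accepting of everything.** The bias of a mean is (share missing) × (score gap).
- Group A: USS+CLC(d) is completed by 75.7%; the two USS+SAP(d) phases average (83.1 + 69.0)/2 = 76.0%.
- Group B: USS+CLC(d) is completed by 83.1%; the two USS+SAP(d) phases average (91.1 + 75.7)/2 = 83.4%.

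The shares differ by about 0.3 percentage points. For an assumed gap of 1 to 2 SD, the bias in the contrast is about 0.003 to 0.007 SD, which is negligible.

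**If the dislike is specific to USS+CLC(d).** Bias ≈ 0.089 × q × d, where q is the share of those exits that are system-related and d is the gap in the USS+CLC(d) score not already visible in the subject's USS+SAP(d) score. Neither is in the documents. For scale only:

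| | d = 0.25 SD | d = 0.5 SD | d = 1 SD |
|---|---|---|---|
| q = 1 | 0.02 | 0.04 | 0.09 |
| q = 0.5 | 0.01 | 0.02 | 0.04 |

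For two conditions, f = 0.35 to 0.4 corresponds to 2f = 0.70 to 0.80 SD. Section 6.2 does not say which SA3 contrast that refers to, and the predicted inferiority in SA3(2) has no number.

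**The attrition signal.** If 0%, 25%, 50% or 75% of the 34 losses are unrelated to acceptance (assumed), then 34, 25.5, 17 or 8.5 carry information on it. The eight stopping rules divide into one subject request, two behavioural rules (persistent non-contact, persistent non-adherence), two that allow return (glucocorticoids; ketones or illness), and three others (malfunction, repeated severe glycemic events, pregnancy).

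**The case against.** A reader might infer that acceptance is overstated, and even that the SA3(2) difference is driven to zero or reversed. The documents do not support that. It requires leavers to be less accepting of USS+CLC(d) in particular; a general dislike nearly cancels in the contrast. No score gap is given anywhere. The 31% is an upper limit, and randomization (section 3.2) precedes the training and run-in visits, so part of the loss may fall outside the treatment phases.

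A reader might also infer from the stopping rules that seven of eight exits are not the subject's choice. Counting rules is not counting withdrawals: subject request could account for most losses, the two behavioural rules may express low acceptance, and two rules allow return. Nor does section 6.1 equate attrition with acceptance. Scores and interviews remain the main comparison, and attrition is supplementary.

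The two halves of the point also trade off. The more exits are forced, the smaller the score bias; the more are system-related, the cleaner the attrition signal. They cannot both apply at full strength.

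Finally, the acceptance questionnaire's timing is loosely stated in section 3.1, the questionnaire appendix is not available for this review, and a mixed model keeps leavers' earlier scores. These limit the point without removing it. A mixed model would predict the missing USS+CLC(d) score from earlier scores and from those who stayed, not from the reason for leaving. No text describes an assessment at exit or an analysis by reason.

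**Conclusion.** The point holds as a gap in data collection and analysis. On the schedule as written, subjects who leave during USS+CLC(d) give no acceptance score for it. If they leave because of its complexity, the SA3(2) inferiority may be understated; the documents do not allow the amount to be estimated. The tabulated 0.01 to 0.09 SD rests entirely on assumed q, d and equal loss per phase. It could matter only if the true difference is small.

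Separately, the SA3 attrition analysis as written would mix duration-related and forced exits with exits over the system. That follows from sections 1.5.1, 5.10.1 and 6.1 and needs no assumption about scores; how strongly the signal is diluted is unknown. The sample size is unaffected.

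**What to change.** 1. At withdrawal, offer the existing technology acceptance questionnaire and a phone interview, assigned to the phase in progress. Exit HbA1c and device download are not needed for SA3.
2. In section 6.1, classify the dropout reasons already gathered under section 5.6 as subject-initiated and system-related, behavioural or ambiguous (non-contact, non-adherence), or other and forced. Tabulate them by phase and sequence. Base the SA3 reading of attrition on the first class, add the second in a sensitivity analysis, and report the third separately. Do not count a temporary stop followed by return as attrition.
3. Add a sensitivity analysis of the SA3(2) contrast in which missing USS+CLC(d) scores of system-related leavers are assumed lower over a stated range.

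The cost is a short amendment. Questionnaires may already be completed electronically (section 3.1) and interviews held by phone (section 3.7), so no new instrument is needed. Some leavers will decline, and classifying reasons needs some judgement. Scores not collected at exit are hard to recover later.
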